7.7.3 Pharmacogenetics

7.7.3.1 Pharmacogenetics Endpoints

Exploratory pharmacogenetics (PGt) studies may be performed if significant Pharmacokinetic/Pharmacodynamic (PK/PD) relationships are observed or adverse events are identified. Genomic markers of disease may also be investigated. Pharmacogenetic studies will be conducted with Biostatistics design and analysis and compared to PK/PD results or clinical outcomes.

CYP2C19 exhibits genetic polymorphism, which can cause large differences in the pharmacokinetics of VOR. Individuals are classified as either extensive metabolizers or poor metabolizers of this enzyme, and the distribution of these genotypes varies greatly across different populations. Exploratory analysis genetic testing of the CYP2C19 polymorphisms and PK/PD, safety and efficacy relationships may be conducted as the data allow.

7.7.3.2 PD/PGt, PK/PGt and Safety/PGt Analysis

Pharmacogenetic interrelationships may be explored.

7.7.4 Other Endpoints

Sparse pharmacokinetic (steady state trough) sampling will be performed on all subjects throughout the treatment period. Food intake data at the time of POS tablet administration will be collected to evaluate the effect of food intake on POS steady state pharmacokinetic profile. For adolescents on IV therapy, plasma samples will be collected at the time of completion of their 90-minute infusion at Day 7, Week 2,

Week 4, Week 6 and Week 12 (EOT). These PK samples should be collected via peripheral venipuncture and not be drawn from the central catheter. PK/PD correlation tests assessing achievable serum drug levels of POS and VOR vs. minimum inhibitory concentrations for *Aspergillus* isolates and global clinical response will be conducted on all randomized subjects with available data. Exposure/response assessments will be conducted including an exploration of the relationship between PK/PD indices with efficacy and safety timepoints as available data allow.

7.8 Criteria for Early Termination of the Trial

The clinical trial may be stopped if the extent (incidence and/or severity) of emerging effects/clinical endpoints is such that the risk/benefit ratio to the trial population as a whole is unacceptable. The external Data Monitoring Committee will evaluate the results and safety assessments and can make recommendation for stopping the trial early.

In addition, further recruitment in the trial or at (a) particular site(s) may be stopped due to insufficient compliance with the protocol, GCP and/or other applicable regulatory requirements, procedure-related problems, or the number of discontinuations for administrative reasons is too high.

8.0 STATISTICAL AND ANALYTICAL PLAN

This section outlines the statistical analysis strategy and procedures for the study. If, after the study has begun, but prior to any unblinding, changes are made to primary and/or secondary hypotheses, or the statistical methods related to those hypotheses, then the protocol will be amended (consistent with ICH Guideline E-9). Changes to exploratory or other non-confirmatory analyses made after the protocol has been finalized, along with an explanation as to when and why they occurred, will be listed in the Clinical Study Report (CSR) for the study. Post hoc exploratory analyses will be clearly identified in the CSR. No separate Statistical Analysis Plan (SAP) will be issued for this study.

8.1 Responsibility for Analyses/In-House Blinding

The statistical analysis of the data obtained from this study will be the responsibility of the Clinical Biostatistics department of the SPONSOR.

This study will be conducted as a double-blind study under in-house blinding procedures. The official, final database will not be unblinded until medical/scientific review has been performed, protocol violators have been identified, and data have been declared final and complete.

The Clinical Biostatistics department will generate the randomized allocation schedule(s) for study treatment assignment. Randomization will be implemented in an interactive voice response system (IVRS).

8.2 Hypotheses/Estimation

8.2.1 Primary

Objective: To compare the all-cause mortality for posaconazole (POS) compared to voriconazole (VOR) in the first line treatment of invasive aspergillosis (IA) through Day 42 in all randomized subjects who received at least one dose of study treatment (in the ITT [Intention to Treat] population). (see [Section 8.4.1](#)).

Hypothesis: The all-cause mortality rate through Day 42 in the POS IV/oral 300-mg QD treatment group is non-inferior to that in the VOR IV 4 mg/kg BID/oral 200- mg BID treatment group.

8.2.2 Secondary

Objective: To evaluate the all-cause mortality for POS vs. VOR through Day 42 in the FAS population.

Objective: To evaluate the all-cause mortality for POS vs. VOR through Day 84 in the ITT population.

Objective: To evaluate the all-cause mortality for POS vs. VOR through Day 84 in the FAS population

Objective: To evaluate the adjudicated global clinical response for POS vs. VOR at Week 12 in the FAS population.

Objective: To evaluate the adjudicated global clinical response for POS vs. VOR at Week 6 in the FAS population.

Other secondary objectives are:

- To evaluate time to death (all causes) in subjects with proven or probable IA receiving POS versus VOR.
- To evaluate the mortality due to IA through Day 42 and Day 84 in subjects receiving POS vs. VOR.
- To evaluate the safety and tolerability of POS and VOR by analyzing Tier 1 Safety and all adverse events.
- To evaluate the safety of POS compared to VOR therapy in the All-Patients-as-Treated (APaT) population.

- To evaluate, in the subset of subjects that have pharmacokinetic data and food intake records, the pharmacokinetic profile of POS and VOR, including an evaluation of the effect of food intake on the POS tablet steady state pharmacokinetic profile, and to evaluate the exposure-response (efficacy and safety endpoints) relationships of POS and VOR in a subset of subjects with available data.

8.2.3 Exploratory

- To explore the effects of CYP2C19 polymorphisms and predicted metabolic enzyme activity on POS and VOR plasma concentration.
- To explore pharmacogenetic endpoints and their association with key efficacy and safety parameters.
- To explore the effect of treatment on serological biomarkers (e.g., galactomannan EIA, beta-D-glucan).

Please note the analyses to test the above three exploratory objectives may be conducted at a later date, as data allow.

8.3 Analysis Endpoints

Efficacy and safety endpoints that will be evaluated for within- and/or between-treatment differences are listed below, followed by the descriptions of the derivations of selected endpoints.

8.3.1 Efficacy/Pharmacokinetics Endpoints

A description of efficacy measures is provided in [Section 7.7.1](#).

8.3.2 Safety Endpoints

An initial description of safety measures is provided in [Section 7.7.2](#).

The analysis of safety results will follow a tiered approach. The tiers differ with respect to the analyses that will be performed. Safety parameters or adverse experiences of special interest that are identified *a priori* constitute “Tier 1” safety endpoints that will be subject to inferential testing for statistical significance with p-values and 95% confidence intervals provided for between-group comparisons. Other safety parameters will be considered Tier 2 or Tier 3. Tier 2 parameters (requires that at least 4 patients in any treatment group exhibit the event) will be assessed via point estimates with 95% confidence intervals provided for between-group comparisons; only point estimates by treatment group are provided for Tier 3 safety parameters.

The following four categories are Tier 1 events[†]:

- Hepatic safety: Elevated AST or ALT lab value that is ≥ 3 x the upper limit of normal (ULN) and an elevated total bilirubin lab value that is ≥ 2 x ULN and, at the same time, an alkaline phosphatase lab value that < 2 ULN, as determined by way of protocol-specified laboratory testing or unscheduled laboratory testing;
- CNS and visual safety: Treatment-emergent adverse events (TEAEs) related to visual and CNS disturbances. See [Section 8.5.2](#) for a list of terms
- Dermatologic reactions: TEAEs including rash and photosensitivity rash;
- Adrenal steroidogenesis: TEAEs indicating adrenal insufficiency or temporally associated TEAEs of hypotension.

[†] The team has listed specific terms, see section 8.5.2, that they believe fall under these broader categories, however these categories may include additional related terms when full data reporting for the study is complete.

The following are Tier 2 events based on specific AE categories: (1) at least one adverse experience; (2) drug related adverse experience; (3) serious adverse experience; (4) serious and drug related adverse experience; (5) discontinued study therapy due to an adverse experience.

8.4 Analysis Populations

This study will investigate two extended spectrum azoles (POS and VOR) in subjects with proven or probable IA based on modified 2008 EORTC/MSG definitions. Subjects with possible IA may also be enrolled into the study with further evaluation of proven or probable IA.

8.4.1 Efficacy Analysis Populations

The Intention to Treat (ITT) population will serve as the primary population for the analysis of all-cause mortality through Day 42 in this study. The ITT population consists of all randomized subjects who received at least one dose of study treatment.

The Full Analysis Set (FAS) population will serve as the secondary population for the analysis of efficacy data in this study. The FAS population consists of all randomized subjects who have been classified as having proven or probable IA (based upon independent adjudication assessment using the modified 2008 EORTC/MSG definitions), and receive at least one dose of study drug.

Subjects will be included in the treatment group to which they are randomized for the analysis of efficacy data using the ITT and FAS populations. Details on the approach to handling missing data are provided in [Section 8.5](#) Statistical Methods.

8.4.2 Safety Analysis Populations

The All Patients as Treated (APaT) population will be used for the analysis of safety data in this study. The APaT population consists of all randomized subjects who received at least one dose of study treatment. Subjects will be included in the treatment group corresponding to the study treatment they actually received for the analysis of safety data using the APaT population. For most subjects this will be the treatment group to which they are randomized. Subjects who take incorrect study treatment for the entire treatment period will be included in the treatment group corresponding to the study treatment actually received.

At least one laboratory or vital sign measurement obtained subsequent to at least one dose of study treatment is required for inclusion in the analysis of each specific parameter. To assess change from baseline, a baseline measurement is also required.

Details on the approach to handling missing data for safety analyses are provided in [Section 8.5](#) Statistical Methods.

8.5 Statistical Methods

Statistical testing and inference for safety analyses are described in [Section 8.5.2](#). Efficacy results that will be considered to be statistically significant after consideration of the strategy for controlling the Type I error are described in [Section 8.6](#), Multiplicity. Nominal p-values may be computed for other efficacy analyses as a measure of strength of association between the endpoint and the treatment effect rather than formal tests of hypotheses. For both the efficacy and safety analyses, unless otherwise specified, all statistical tests will be conducted at $\alpha=0.05$ level (two-sided).

8.5.1 Statistical Methods for Efficacy Analyses

All-Cause Mortality

The primary endpoint, corresponding to the primary trial objective, is all-cause mortality through Day 42 in subjects in the ITT population.

The primary analysis is to compare the POS arm to the VOR arm. The difference in mortality rate between arms (POS minus VOR) and the associated 95% confidence interval (CI) on the difference will be calculated using Miettinen and Nurminen's method [13] stratified by risk for mortality/poor outcome (high risk, not high risk). If the upper limit of that CI is less than 10% (the non-inferiority margin), then non-inferiority of POS will be declared. If non-inferiority is declared, it can be further concluded that POS is superior to VOR if the lower limit of the CI exceeds zero. Due to the principle of closed testing, no adjustment for multiplicity is required since non-inferiority can always be concluded whenever the data also supports superiority. Summary statistics and a tabulated treatment comparison will be provided.

Other secondary endpoints include all-cause mortality through Day 42 and Day 84 for the FAS population and will be evaluated using similar methodology as will be used for the primary endpoint in the ITT population.

Mortality will be evaluated through Day 42 and through Day 84 with no time window applied either before or after the target day.

Survival will also be assessed using Kaplan-Meier methodology and compared between the two arms using the Log-Rank test stratified by risk for mortality/poor outcome (high risk, not high risk).

Proportion Of Subjects Achieving Global Clinical Response

A secondary endpoint is global clinical response (partial or complete response defined by the 2008 MSG/EORTC criteria) at 6 weeks post-randomization in the FAS population.

The analysis is to compare the POS arm to the VOR arm. The difference in proportions between arms (POS minus VOR) and the associated 95% confidence interval (CI) on the difference will be calculated using Miettinen and Nurminen's method [13] stratified by risk for mortality/poor outcome (high risk, not high risk). For the analysis, missing or unable to determine responses will be considered as failures.

An assessment between the two treatment arms will be performed on ITT subjects that are excluded from the FAS, looking at potentially key baseline prognostic factors, such as the stratification variable of risk status for mortality/poor outcome.

As one of the secondary endpoints, the global clinical response at Week 12 in the FAS population will be analyzed in a similar manner.

Global clinical response at Week 6 and Week 12 will be evaluated to include the completion of the response components within the visit windows, ± 2 weeks for Week 6 and ± 4 weeks for Week 12.

See [Appendix 7](#) for detailed analysis methods and modeling procedures.

[Table 13](#) summarizes the key efficacy analyses.

Table 13 Analysis Strategy for Key Efficacy Variables

Endpoint/Variable (Description, Time Point)	Primary vs. Supportive Approach ^a	Statistical Method	Analysis Population	Missing Data Approach
Primary Endpoint				
All-cause mortality through Day 42	P	95% CI ^b to test for non-inferiority and if established, test for superiority	ITT	M=F ^c
Secondary Endpoints				
Proportion of subjects achieving global clinical response at Week 6 and 12	P	95% CI ^b	FAS	M=F ^c
All-cause mortality through Day 42 and Day 84	P	95% CI ^b	FAS	M=F ^c
All-cause mortality through Day 84	P	95% CI ^b	ITT	M=F ^c
Time to all-cause mortality	S	Kaplan-Meier product-limit estimates; stratified Log-rank test	FAS	Right Censoring
Mortality due to IA through Day 42 and Day 84	S	95% CI ^b	FAS	DAO

^a P=Primary approach; S=Secondary approach.

^b Miettinen and Nurminen's method [13] with stratification by risk status for mortality/poor outcome (high/not high).

^c Missing or 'unable to determine' responses will be considered as failures.

^d M=F: Missing = failure; DAO=Data as observed.

The strategy to address multiplicity issues with regard to multiple treatment comparisons, multiple [efficacy] endpoints, multiple timepoints, and/or interim analyses is described in [Section 8.6](#), Multiplicity and [Section 8.9](#), Interim Analyses.

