Randomization: Subjects will be randomly assigned (in a 1:1 ratio) to receive either POS or VOR according to a computer-generated randomization schedule using the interactive voice response system (IVRS).

Stratification: Subjects will be stratified prior to treatment assignment by risk status for mortality/poor outcome.

High Risk: Any one of the following are present at Baseline or in the patient's medical history:

- Allogeneic hematopoietic stem cell transplant (HSCT).
- Relapsed leukemia, undergoing salvage chemotherapy.
- Liver transplant recipients [12].

Not High Risk: Any other eligible subject (none of the high-risk criteria are present at Baseline or in the subject's medical history)

Data Sets to be Analyzed: The primary analysis will be performed on the ITT population. The ITT population consists of all randomized subjects who have received at least one dose of study drug. Secondary analyses will be based on the FAS population which includes subjects with confirmed proven or probable IA (based on 2008 modified EORTC/MSG definitions) and who: 1) receive at least one dose of study treatment; 2) have at least one post-randomization observation for the analysis endpoint subsequent to at least one dose of study treatment; 3) have baseline data for those analyses that require baseline data. Safety analyses will be based on the all-patients-as-treated (APaT) population, which includes all subjects who received at least one dose of study treatment. The FAS population consists of all randomized subjects who have at least one post-randomization observation for the analysis endpoint subsequent to at least one dose of study treatment (and have baseline data for those analyses requiring baseline data).

Sample Size: Approximately 600 subjects will be enrolled in this study, receive study drug and be randomly assigned in a 1:1 ratio to receive either POS or VOR. This sample (approximately 300 randomized subjects in each azole arm) will have ~ 82.7% power (with 1-sided alpha=0.025) to show non-inferiority of POS compared to VOR using a 10% margin assuming an all-cause mortality through Day 42 of 23% for both treatment groups. This assumed rate is based on a meta-analysis of historical VOR mortality data [27]. If the criteria for non-inferiority are met, then a superiority analysis of POS over VOR will be assessed.

Efficacy Analysis:

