8.5.3 Summaries of Baseline Characteristics, Demographics, and Other Analyses

Demographic and Baseline Characteristics

The comparability of the treatment groups for each relevant characteristic will be assessed by the use of tables and/or graphs. No statistical hypothesis tests will be performed on these characteristics. The number and percentage of subjects screened, randomized, the primary reasons for screening failure, and the primary reason for discontinuation will be displayed. Demographic variables (e.g., age, gender, race, etc.), baseline characteristics, primary and secondary diagnoses, and prior and concomitant therapies will be summarized by treatment either by descriptive statistics or categorical tables.

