8.6 Multiplicity

Efficacy

No multiplicity adjustment is necessary as there is only one primary efficacy hypothesis based on a single efficacy endpoint at a single timepoint. Statistical significance in this setting is equivalent to nominal significance and will be based on a one-sided alpha level of 0.025.

If non-inferiority is declared, it can be further concluded that POS is superior to VOR if the lower limit of the CI exceeds zero. Due to the principle of closed testing, no adjustment for multiplicity is required since non-inferiority can always be concluded whenever the data also supports superiority.

Safety

No multiplicity adjustment will be used for the safety analysis.

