8.8 Subgroup Analyses and Effect of Baseline Factors

To determine whether the treatment effect is consistent across various subgroups, the estimate of the between-group treatment effect (with a nominal 95% CI) for the primary endpoint will be estimated and plotted within each category of the following classification variables:

- Region (US, Ex-US)
- Sex (female, male)
- Age among adults (≥ 18 years to \leq median of adults, $>$ median of adults)
- Ethnic Origin (Black, White, Other) and (Hispanic, Non-Hispanic)
- Risk status for mortality/poor outcome (high risk, not high risk).
- Patients population: (1) proven vs. probable IA; (2) site of IA infection (lung, sinus, multiple sites, etc.); (3) underlying disease; (4) neutropenic status at baseline (ANC < 500 vs. > 500)

The consistency of the treatment effect will be assessed descriptively via summary statistics by category for the classification variables listed above.

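### The primary Day 42 risk difference is valid but adjusts only for the two-level risk stratum, leaving recorded and plausibly prognostic baseline variables unused; the precision gain available depends on assumption.

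*Combined protocol and SAP*

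**What the plan says.** The primary endpoint in Section 8.5.1 is "all-cause mortality through Day 42 in subjects in the ITT population". The POS minus VOR difference and its 95% interval come from the Miettinen-Nurminen method, "stratified by risk for mortality/poor outcome (high risk, not high risk". Table 13, footnote b, repeats this. The decision rule is "If the upper limit of that CI is less than 10% (the non-inferiority margin), then non-inferiority of POS will be declared", and Section 8.6 says that significance "will be based on a one-sided alpha level of 0.025".

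Section 7.4.1.2 defines high risk as allogeneic HSCT, relapsed leukemia under salvage chemotherapy, or liver transplant. Everyone else is not high risk.

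Other baseline data appear in two places in the analysis plan:

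- Section 8.5.3 summarizes "Demographic variables (e.g., age, gender, race, etc.), baseline characteristics, primary and secondary diagnoses" by arm.
- Section 8.8 gives descriptive subgroup estimates for the primary endpoint by age, underlying disease and "neutropenic status at baseline (ANC < 500 vs. > 500", among other factors.

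Section 8.5.1 points to Appendix 7 for modelling procedures. Appendix 7 contains no model. It gives only the two-proportion Miettinen-Nurminen interval in unstratified form.

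The Synopsis states about 82.7% power with "approximately 300 randomized subjects in each azole arm", "using a 10% margin assuming an all-cause mortality through Day 42 of 23% for both treatment groups".

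**The concern.** Non-inferiority turns entirely on where the upper confidence limit falls. Baseline variables that predict death by Day 42 could shorten that interval without any further enrolment. Three candidates (age, baseline ANC, underlying disease) are already collected, and the plan uses none of them in the deciding estimate.

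The spare precision is modest. Table 17 gives 82.7% power at 300 per arm, 80.8% at 285 and 78.6% at 270, all at 23% mortality in both arms. With a true difference of +1 point, power at 300 per arm is 73.7%.

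There is a second, smaller stake. If the upper limit lands close to 10% and the arms differ by chance in age or neutropenia, an adjusted analysis will be wanted. Without pre-specification, its covariates would be chosen after the result is known.

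**Working it through.** **Inputs from the documents.** Mortality 23% in both arms, n = 300 per arm, margin 0.10, one-sided alpha 0.025 (Synopsis, Sections 8.6 and 8.7.2).

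**Step 1: reproduce the stated power.** I use the Farrington-Manning form, which is consistent with Miettinen-Nurminen:

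power = Φ[(0.10 − 1.96·se0)/se1]

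- se1 = √(2 × 0.23 × 0.77/300) = 0.03436.
- se0 uses the rates constrained to differ by 0.10, which are 0.2874 and 0.1874: √[(0.2874 × 0.7126 + 0.1874 × 0.8126)/300] = 0.0345.
- 0.10/0.03436 = 2.910 and 1.96 × 0.0345/0.03436 = 1.968, so power = Φ(0.942) = 82.7%, as stated.

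The same formula gives 80.8% at 285 and 78.6% at 270 per arm, matching Table 17. These figures credit neither covariates nor the stratum.

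**Step 2: what the stratum already recovers.** The documents give neither the share of high-risk subjects nor their mortality. If a share π is high risk and mortality differs by d between strata, the stratum explains π(1−π)d²/(0.23 × 0.77) of the outcome variance. For π from 20% to 50% and d from 5 to 20 points, that is 0.2% to 5.7%. Further covariates count only for what they add beyond this.

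**Step 3: effect of removing a further share r of the variance.** Both standard errors shrink by √(1−r), so power = Φ[2.910/√(1−r) − 1.968] at 300 per arm. At 270 per arm, 2.910 becomes 2.761. This is a large-sample approximation, and r is an assumption.

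| r (assumed) | √(1−r) | Power, 300/arm | Power, 270/arm | Power, 300/arm, true +1 point | Equivalent n per arm, 300/(1−r) |
|---|---|---|---|---|---|
| 0 | 1.000 | 82.7% | 78.6% | 73.7% | 300 |
| 2% | 0.990 | 83.4% | 79.4% | 74.6% | 306 |
| 4.2% | 0.979 | 84.3% | 80.3% | 75.5% | 313 |
| 7.8% | 0.960 | 85.6% | 81.8% | 77.1% | 325 |
| 12% | 0.938 | 87.2% | 83.5% | 79.0% | 341 |

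The lower three rows correspond to a full model with AUC of about 0.65, 0.69 and 0.73, if 30% of subjects are high risk with a log-odds of 0.5. In the same set-up, an AUC of 0.62 gives a gain of about 0.8 point and 0.58 gives about 0.3 point. The low end of the range is therefore close to zero.

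The gains in the table, starting from 82.7%, are 1.6, 2.9 and 4.5 points for the lower three rows. Crediting the stratum first, as the plan's analysis does, raises the starting power slightly and leaves the increments at about 1.5 to 4.5 points.

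**Step 4: near the margin.** The Miettinen-Nurminen interval for 78/300 vs 69/300 is (−3.9, 9.9), as in Section 8.7.2. For 79/300 vs 69/300 the difference is 3.33 and the upper limit is 10.23, a distance of 6.90.

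- A 4% shorter interval gives 3.33 + 0.96 × 6.90 = 9.96, which meets the margin.
- A 2% shorter interval gives 3.33 + 0.98 × 6.90 = 10.09, which does not.

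This holds the point estimate fixed, whereas adjustment also moves it, in either direction. It shows scale only.

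**The case against.** The strongest reply is that nothing is wrong. The analysis is valid, pre-specified and matched to the randomization stratum. Its stated power exceeds the 80% reference in Section 8.7.2 before any covariate gain is counted. All of that stands. Chance imbalance is not bias either, because under randomization the confidence interval already allows for it.

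A reader might infer that the plan discards strong predictors. The documents do not support this: they give no mortality by age, ANC or underlying disease, and no R² or AUC. Section 8.8 does not fill the gap. Its purpose is consistency of the treatment effect, and the same list holds region, sex and ethnic origin. Section 8.5.1 does speak of key prognostic factors with the stratum as an example, but only for comparing subjects excluded from the FAS, and it names no others.

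Overlap is a fair point too. Two of the three high-risk criteria are transplant types and the third is a leukemia state, so an underlying-disease covariate may largely repeat the stratum.

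Changing the method of the primary hypothesis also has a cost. Section 8.0 requires a protocol amendment, Section 9.1.1 brings in ethics review as appropriate, and up to 155 centers are planned. A late change that mainly shortens the interval may be questioned. This argues for doing it before unblinding with a short fixed covariate list, or for the supporting-analysis option. It does not remove the point.

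**Conclusion.** The point holds as an efficiency gain whose size rests on assumption. The deciding estimate adjusts for one binary factor, other plausibly prognostic variables are recorded, and no adjusted mortality analysis is specified.

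The likely benefit runs from almost nothing to about 4.5 power points at 300 per arm. At 270 per arm, removing as little as 4.2% of the remaining variance would bring power from 78.6% back above 80%. These figures assume 23% mortality in both arms, large-sample variance scaling, and values of r that the documents neither give nor contradict.

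It would go too far to conclude that the primary analysis is biased, that the trial is underpowered at its planned size, or that adjustment would turn a narrowly failed result into a success. The first two conflict with the design and with the stated 82.7%. The third fails at a 2% shortening and ignores movement of the point estimate.

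**What to change.** By protocol amendment before unblinding, specify the following in Section 8.5.1 and Appendix 7:

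- **Estimator.** The marginal POS minus VOR Day 42 risk difference, standardized (g-computation) from a logistic model, with a robust or influence-function 95% interval compared with 10%. The endpoint, the ITT population and the missing-as-failure rule stay as they are. The estimate remains a marginal difference, so the margin justification in Section 8.7.1 is untouched.
- **Covariates.** Treatment, risk stratum, age, baseline ANC (<500 vs ≥500, since Section 8.8 leaves exactly 500 unplaced) and a short, defined underlying-disease category that does not duplicate the stratum. With about 138 expected deaths (23% of 600), the list should stay short.
- **Rules.** A stated rule for missing baseline covariates, and stratified Miettinen-Nurminen as supporting analysis and as fallback if the model does not converge.

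If the sponsor prefers to keep the primary method, the same adjusted interval can be a named supporting analysis. That fixes the covariates in advance and checks robustness to chance imbalance, but it does not raise the power of the primary test.

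The cost is the amendment, one further program and the two extra rules. No new data are needed.
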